In our study, a factorial design with 2 design variables (Cesarean Delivery Method [Gentle, Traditional] and Preference of Method [Gentle, Traditional]) will be used. A sample size of 508 total patients (127 patients in each of the 4 Method x Preference combinations) has been determined necessary to detect a 0.5-point difference in mean satisfaction scores (on a 5-point scale) and a 15-minute difference in time-to-initiation of family bond between the 2 groups of each design variable, given 2-factor generalized linear modeling with normally-distributed (or log-transformed) responses, standard deviation of 2 points (for satisfaction score) and 1-hour (for family bond initiation), alpha of 0.05, and power of 0.80. Moreover, to detect a 15% difference in probability of breastfeeding prior to discharge between the 2 groups of each design variable using logistic regression, a sample size of 432 total patients (108 patients in each of the 4 Method x Preference combinations) would be necessary. To detect clinically-relevant differences for all outcomes (responses) of interest in the Primary and Secondary Objectives, we will target 508 total patients.

VI. DESCRIPTION OF DELIVERY METHODS

Method 1: Family-centered cesarean

Standard preoperative preparation will be performed in the patient's room, including surgical site hair clipping, chlorhexidine wash (at ASMC only), IV placement, completion of pre-procedure operating room checklist, and administration of prophylactic antibiotics, antiemetics (at ASMC only), and fluids. The patient will then be taken to the operating room. The pulse oximeter will be placed on the mother, and the electrocardiogram leads will be placed away from anterior chest wall or via an EKG back-patch to allow space for newborn and mom skin contact. Regional spinal anesthesia will be administered in normal fashion. The mother will lie down on the bed and, once sufficient anesthesia block is obtained, her gown will be removed and a blanket will be provided for her to cover her chest, allowing for easier skin-to-skin contact after delivery. Prior to the lowering of the drape, the mother's head will be elevated. Fetal heart tracing will be monitored until adequate block is obtained to confirm fetal well-being.

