Preoperative preparation will continue with abdomen preparation. We will then wait 3 minutes from wash to dry before placing the blue drape on the mother's abdomen and attaching it to the IV poles, thereby screening the mother from the entire surgery. After delivery, the newborn will be handed off to a nurse waiting at the side of the mother who will take the newborn to the warmer on the opposite side of the operating room. The newborn will be dried and warmed with fresh towels on the warmer, while being evaluated by the nurse and respiratory therapist per hospital cesarean section protocol. The nurse will then proceed with newborn measurements, weight, bath, and administration of vitamin K and erythromycin ointment. The newborn will be swaddled and kept in the warmer until the mom requests that the newborn be brought to her or until the surgery has been completed and the mom is ready to be transferred to the recovery room.

VII. DATA COLLECTION

Patients will be followed throughout their hospital stay. The following variables of interest will be retrospectively collected from EPIC or recorded during the surgery on the OR Worksheet (* - Note, the OR Worksheet was updated on 2/16/2018.):

Maternal Variables of Interest

- Medical record number
- Date of birth
- Delivery Hospital (0=ASMC; 1=ABMC)
- Date of consent for scheduled cesarean section
- Date of procedure
- Calculated maternal age
- Race
- Ethnicity
- Gravidity (Gx)
- Parity (Pxxxx)
- Gestational Age (XwXd)
- Height (inches)
- Weight (lbs)
- Calculated BMI (kg/m²)
- History of previous vaginal delivery (0=No; 1=Yes)
- History of previous cesarean delivery (0=No; 1=Yes)
- Reason for previous cesarean delivery
- History of previous abdominal/pelvic surgery (0=No; 1=Yes)
- Reason for planned cesarean delivery
- Type of cesarean delivery technique (0=Family-centered; 1=Traditional)
- Identified mother preference (0=Family-centered; 1=Traditional)
- Type of cesarean delivery (0=NA; 1=Classical; 2=Low Transverse)
- Type of skin incision (0=NA; 1=Pfannenstiel; 2=vertical)
- Operative start time (00:00:00)
- Operative stop time (00:00:00)
- Duration of operation (minutes)
- Estimated blood loss (mL)
- Hemorrhage EBL >1000mL (0=No; 1=Yes)
- Complications occurred (0=No; 1=Yes)
- Type(s) of complication(s) that occurred
- If the mother's delivery technique was family-centered, was she switched to a traditional cesarean? (0=No; 1=Yes)*
- Was mom offered to view the birth of her baby? (0=No; 1=Yes)*

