- If offered to view the birth of her baby, was the drape dropped? (0=No; 1=Yes)*
- Was mom/other support person offered baby right away? (0=No; 1=Yes)*
- Physician Name
- Did family bond occur in the OR? (0=No; 1=Yes)*
- Time from birth to initiation of family bond (minutes)*
- Person who initiated family bond (0=Mother; 1=Father; 2=Other Support Person)*
- Family bond interrupted in the OR (0=No; 1=Yes)*
- Reason family bond interrupted in the OR*
- If the family bond DID NOT occur, why not?*

-
- Surgical site infection associated with this surgery (0=No; 1=Yes)
 - Time to skin-to-skin contact & all other related skin-to-skin variables identified
 - Breastfeeding status flowsheet data (3=Unknown; 2=No; 1=Yes)

Neonatal Variables of Interest

- Birth weight
- 1-min APGAR
- 5-min APGAR
- Documented neonatal infection (0=No, 1=Yes)
- Newborn heart rate at 10 minutes*
- Newborn respiratory rate at 10 minutes*
- Newborn temperature at 10 minutes*
- Time taken for newborn to reach oxygen saturation >90%*

Assessment of patient satisfaction will be conducted following delivery. Questions from an 11-item questionnaire will be asked of the patient by the study coordinator, [name], or one of the resident physicians or the nurses/charge nurses at ASMC and study coordinator, [name], or one of the nurses or charge nurses at ABMC. Please see the questionnaire displayed in a separate document.

Please note, that while we aim to obtain the OR worksheet and patient satisfaction survey from all patients enrolled in the study, there may be circumstances in which one or the other were not completed. If a patient has either the OR worksheet or the patient satisfaction survey completed, we will not exclude them from the study/analyses, but it will be adjusted for.

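### Time to family bond is tied to a form filled in during surgery, with no rule for first contacts after the operating room, which are likelier under Method 2; a worksheet-only analysis would understate the difference

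*Combined protocol and SAP*

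**What the plan says.** Section V includes among its targets "a 15-minute difference in time-to-initiation of family bond between the 2 groups of each design variable", with "standard deviation of 2 points (for satisfaction score) and 1-hour (for family bond initiation" and "alpha of 0.05, and power of 0.80". The secondary objective in Section II treats skin-to-skin contact and family bond initiation as the same thing.

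Section VII names two sources: "The following variables of interest will be retrospectively collected from EPIC or recorded during the surgery on the OR Worksheet". The asterisk is attached to the worksheet. Under the maternal variables, "Time from birth to initiation of family bond (minutes" is starred. So are the items on whether the bond occurred in the operating room, who started it, whether it was interrupted there and, if it did not occur, why not. A separate time to skin-to-skin contact is listed without an asterisk. Follow-up covers the hospital stay.

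In Section VI, Method 1 places the newborn straight on the mother's chest or with her support person. Method 2 keeps the newborn on the warmer until the mother asks, or "until the surgery has been completed and the mom is ready to be transferred to the recovery room". Section VIII analyses times with a lognormal mixed model and mentions no censoring.

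**The concern.** A time endpoint has to be observable for as long as the event can plausibly happen, and to the same extent in both arms. Here the powered endpoint is linked by name to a form described as belonging to the operation, while the control procedure allows first contact to slip to the end of the operation. A woman whose first contact comes in recovery would have a reason for no bond on the worksheet but no time. An uncensored lognormal model can only leave her out.

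Such omissions would depend on both arm and outcome: the longest waits go missing, and Method 2 is where long waits are expected. The comparison would be pulled toward no difference on the outcome that the family-centered method most directly targets. Section VII promises an adjustment when the worksheet or the survey was not completed. That does not cover a completed worksheet whose bond began later.

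**Working it through.** **1. The plan's own figure.** Inputs from Section V: difference 15 minutes, SD 60 minutes, alpha 0.05, power 0.80, 508 women, hence 254 per Method.

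- Normal approximation, two-sided: SE = 60 × √(2/254) = 5.32; 15/5.32 = 2.817; power = Φ(2.817 − 1.960) = 0.804.
- F test for a main effect in a 2 × 2 design: 127 per cell, 508 in total, power 0.803.

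The 508 reproduces. Satisfaction has the same standardised effect (0.5/2 = 15/60 = 0.25), so it requires 508 by itself.

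**2. From endpoint to data item.** Section V's wording matches the starred family-bond time. Section II would equally admit the unstarred skin-to-skin time. No sentence says which one is analysed, or that one fills in for the other.

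**3. What each woman contributes if only the worksheet is used.**

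| First contact | Likelier under | Recorded | In the lognormal model |
|---|---|---|---|
| At once, in the operating room | Method 1 | time | yes |
| On request, in the operating room | Method 2 | time | yes |
| After leaving the operating room | Method 2 | reason only | no |

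**4. Direction of the bias.** Suppose no Method 1 times are lost and a share p of Method 2 times is. The true Method 2 mean is (1 − p) × (mean recorded) + p × (mean late). The recorded difference is then the true difference minus p × (mean late − mean recorded). Late times exceed recorded ones, so the difference is understated whenever p > 0. The documents give neither p nor the late mean, so this cannot be turned into a number for this trial.

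**5. Illustration only.** Assumptions not in the documents: lognormal times with means of 30 minutes (Method 1) and 45 minutes (Method 2), and a recording window of T minutes after birth beyond which times are dropped. The SD of 60 and the difference of 15 are Section V's.

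For mean m, σ² = ln(1 + 60²/m²) and μ = ln m − σ²/2. This gives σ = 1.269, μ = 2.596 for m = 30 and σ = 1.011, μ = 3.296 for m = 45. With z = (ln T − μ)/σ, the recorded share is Φ(z) and the mean of recorded times is m × Φ(z − σ)/Φ(z).

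| T (min) | Recorded, Method 1 | Recorded, Method 2 | Mean recorded, Method 1 | Mean recorded, Method 2 | Difference |
|---|---|---|---|---|---|
| 30 | 74% | 54% | 10.70 | 15.15 | 4.4 |
| 45 | 83% | 69% | 13.61 | 19.90 | 6.3 |
| 60 | 88% | 79% | 15.83 | 23.65 | 7.8 |
| 120 | 96% | 93% | 21.19 | 32.86 | 11.7 |

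With Method 1 means from 15 to 45 minutes and windows from 45 to 120 minutes, 4% to 47% of Method 2 times and 2% to 31% of Method 1 times are lost, and the 15 minutes appears as about 5 to 12. Simulated power stays at or above 0.99 in all these cases, so the harm is an understated difference and not lost power.

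The illustration fits Section VI imperfectly. At T = 30 it loses 26% of Method 1 times, although Method 1 is meant to give contact at once.

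**The case against.** The strongest reply is that nothing in the documents shows the form closing. The worksheet is not included. The family-bond time, unlike two of its neighbours, carries no operating-room limit in its wording, so a later time might be enterable. EPIC is named as a source, follow-up spans the stay, and the unstarred skin-to-skin time could hold every later contact. Method 2 allows contact on request, its end point is readiness for transfer, which comes before she leaves the operating room, and a father or other support person may start the bond. The number of control contacts that fall outside the operating room is therefore unknown and could be small.

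Most of this stands. It means that loss of late times is a consequence of one reading of the plan and not an established fact. It does not settle which variable is the endpoint, or what happens to a woman whose bond starts later.

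A reader might also infer that the 1-hour SD is impossible. A time confined to 0 to T minutes has an SD of at most T/2, so 60 minutes needs a window of at least 120. But the plan gives no length of surgery, and if the endpoint is skin-to-skin time over the stay the bound does not apply. The SD has no stated source, but it is not shown to be wrong. A smaller SD would only raise power for 15 minutes, and satisfaction fixes the 508 regardless.

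**Conclusion.** The point holds as a gap in how the powered secondary time outcome is defined and captured. As written, the plan permits a worksheet-only analysis in which first contacts after the operating room are dropped, mainly from the traditional arm, and the difference is understated. The direction rests on two things in Section VI: Method 1 contact is immediate, and Method 2 contact may wait for the end of surgery.

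The size cannot be derived. The shrinkage of 15 minutes to about 4 to 8 depends on assumed windows of 30 to 60 minutes and assumed means, and should not be cited as the bias in this trial. The documents do not support the stronger statements that late control times are in fact cut off, or that the sample size or stated power is wrong. An amendment is still worthwhile, because it would remove arm-dependent missingness using a variable already on the list.

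**What to change.** In Sections VII and VIII:

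- Name birth to first skin-to-skin contact, over the whole hospital stay, as the single secondary time endpoint in both arms.
- Whenever the worksheet records no bond in the operating room, take the time from the unstarred skin-to-skin variable.
- Record for each woman the source of the time and who initiated contact.
- Keep women with no recorded contact in the analysis as censored, with the censoring time stated, instead of dropping them. A lognormal time-to-event model with the planned physician-within-hospital intercept would retain the percentage-difference interpretation.
- Add a sensitivity analysis by source, for example using the charted time alone for all women. Source will be related to lateness and so to arm.

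The cost is an amendment and a retrospective chart extraction, with no new patients or procedures. It remains feasible although version 11 is dated 3/15/2019 and enrolment is planned to end on 5/31/2019. There are two small drawbacks. Charted times may be coarser than worksheet times, and a bond started by a support person is not the same as maternal skin-to-skin contact; the source and initiator flags are there to separate these. Section V needs no change to the 508 or the stated power.

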Eligible patients will be formally consented on the day of their scheduled cesarean sections by the research coordinator, resident physician(s), charge nurse or nurse. Following enrollment, each patient will be asked to state which method of cesarean delivery she would prefer, if given the option to choose. Preference represents a potential factor influencing patient satisfaction that will be later incorporated into the statistical analysis, based on a 2 x 2 factorial (Method x Preference) design. Documentation of preference at this time (versus following random assignment to cesarean delivery method) is important for minimizing the bias or influence of the random assignment upon the patient’s declared preference.

The patient will be randomized to 1 of the 2 delivery methods by the research coordinator, resident physician(s), charge nurse or nurse, who will present the patient with a sealed envelope. The envelope will contain a slip of paper identifying the patient’s random assignment to either the family-centered cesarean delivery method (Method 1) or the traditional delivery method (Method 2). Fifty percent of all envelopes preassembled for patients will contain paper slips stating “Family-centered”, while the remaining 50% will contain slips stating “Traditional,” allowing for a 1:1 allocation of delivery methods.

Assessment of patient satisfaction following delivery

The primary objective of this study is to compare levels of patient satisfaction with the birthing experience between the two cesarean delivery methods. To assess patient satisfaction, each patient will be verbally surveyed by the study coordinator using an 11-item questionnaire. Similar to the questionnaire used by Armbrust and his colleagues⁶, items on our questionnaire will relate specifically to the mother's birthing experience and answers available per item will be in the form of a modified Likert scale, ranging from 1, the lowest level of agreement or degree of satisfaction, to 5, the highest level of agreement or degree of satisfaction. The survey questions will be asked before discharge (approximately within 48 hours after the delivery), to allow sufficient opportunity for the mother and newborn to bond before discharge.

IV. STUDY POPULATION

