Preoperative preparation will continue with abdomen preparation. We will then wait 3 minutes from wash to dry before placing the blue drape on the mother's abdomen and attaching it to the IV poles, thereby screening the mother from the first part of the surgery. After the fetal head enters the uterine incision, the opaque layer of the drape will be lowered, exposing a transparent drape layer that will enable the mother and her support person to watch the birth. The drape will only be lowered and the rest of the family-centered technique carried out if no complications occur during the operation. In the event of unexpected complications, such as heavy bleeding or problems with delivery of the newborn's head, the surgical drape will not be lowered. Provided that the technique is continued, the newborn's head, followed by the rest of the body, will be delivered by the surgeon in full view of the mother. The umbilical cord will be clamped and cut by the surgeon, and the newborn will then be handed off to the nurse waiting by the mother's

head. The nurse will be holding a sterile drape to receive the newborn and prevent contamination of the surgeon's hands. The nurse will then immediately place the newborn on the mother's bare chest skin, or be given to the mother's support person, where the newborn will be dried and warmed with fresh towels. The opaque layer the drape will then be raised back up, screening the mother from the remaining surgery.

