For each outcome of interest, we will also develop a mixed regression model to examine the fixed main and interaction effects of Method and Preference. All models will be structured with appropriate response distributions, likely including the lognormal (normal distribution with natural log-transformed response) for continuous responses (e.g., time, weight, vitals), multinomial for survey questions of satisfaction, and binomial for 2-category outcomes (e.g., breastfeeding). Following back-transformation or exponentiation of parameter estimates, model results will be interpreted, respectively, as the percentage difference between groups, ratio of odds of a lower value, and ratio of odds of an outcome occurring. Unobserved outcome heterogeneity will be captured by the delivering physician nested within hospital, each combination of which will define a separate random variable and model intercept.

IX. POTENTIAL RISKS AND BENEFITS

Risks associated with Method 1 (family-centered cesarean delivery) include unforeseen patient and/or family discomfort with viewing the surgical field. Patients will be made aware of the potential risk of such discomfort prior to consenting to participating in the study. Notably, risks of this nature are a normal component of any cesarean delivery. Therefore, we will discuss the risk of viewing discomfort with all patients regardless of study participation. An additional risk associated with participating in either method could be loss of confidentiality due to obtaining limited protected health information. However, to minimize risk, all data will be stored on a password protected computer.

A potential benefit of our study is that we may be able gather level-1 evidence to support local, regional, and possibly broader use of a novel method of cesarean delivery, currently being explored nationally and internationally. We hypothesize that there will be improved maternal satisfaction using the family-centered method. We also hypothesize that neonatal morbidity will not be increased and benefits may include earlier skin-skin contact and greater likelihood of breastfeeding.

X. REFERENCES

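### Sections III and VII disagree on who asks the verbal primary-outcome survey, and nothing keeps the interviewer independent of that woman's consent, randomisation or delivery

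*Combined protocol and SAP*

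**What the plan says.** Section III (Assessment of patient satisfaction following delivery) states that "each patient will be verbally surveyed by the study coordinator using an 11-item questionnaire". Answers run from 1 "to 5, the highest level of agreement or degree of satisfaction". The survey is taken before discharge, at roughly 48 hours or less after delivery.

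Section VII (Data Collection) gives a wider list. At the Milwaukee hospital (ASMC) the questions are asked by the study coordinator "or one of the resident physicians or the nurses/charge nurses at ASMC". At the Green Bay hospital (ABMC) they are asked by the study coordinator "or one of the nurses or charge nurses at ABMC"; residents are not listed there.

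Section III (Randomization to Method) has consent obtained "on the day of their scheduled cesarean sections by the research coordinator, resident physician(s), charge nurse or nurse", and then: "The patient will be randomized to 1 of the 2 delivery methods by the research coordinator, resident physician(s), charge nurse or nurse". Section VI describes nurses carrying out the newborn care that separates the methods. Under Method 1, "The nurse will then immediately place the newborn on the mother's bare chest skin", or the newborn goes to the support person. Under Method 2 a nurse takes the newborn to the warmer.

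Section IX gives the study team's expectation: "We hypothesize that there will be improved maternal satisfaction using the family-centered method".

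The variable lists in Section VII include the physician but not the person who asked the survey. The model in Section VIII takes its random intercepts from the physician within each hospital and has no interviewer term. The questionnaire is a separate document and was not supplied.

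**The concern.** The primary outcome is a spoken, subjective rating, given in hospital to whoever asks. The protocol already guards against staff influence at two earlier points: the consent script is worded neutrally, and preference is recorded before allocation. It describes no matching safeguard when the primary outcome is measured.

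Two things are at stake. First, both sections are current text, so a site may follow either, and the permitted interviewers differ by hospital. Second, a woman may be asked how satisfied she was by someone who consented her, handed her the envelope or cared for her newborn. If that affects answers differently under the two methods, the shift enters the treatment comparison directly. A larger sample would not remove it. The listed variables and the planned model would not show it either, because a random intercept for physician within hospital can absorb overall differences in level but not an interviewer effect that differs by arm.

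**Working it through.** **1. The roles side by side**

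| Role | Consents and randomises (III) | Newborn care that differs by method (VI) | Asks survey (III) | Asks survey, ASMC (VII) | Asks survey, ABMC (VII) |
|---|---|---|---|---|---|
| Coordinator | yes (called research coordinator) | not described | yes | yes | yes |
| Resident | yes | not described | no | yes | no |
| Charge nurse | yes | not described separately | no | yes | yes |
| Nurse | yes | yes | no | yes | yes |

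The sections conflict for every role except the coordinator. Every role that may ask the survey is also a role that may consent and randomise. The documents use both study coordinator and research coordinator and do not say whether these are different people. Adopting the Section III wording alone would therefore not secure independence.

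**2. The plan's own figure**

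Inputs from Section V: difference 0.5 points, SD 2, alpha 0.05 (two-sided assumed, since sidedness is not stated), power 0.80.

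n per method = 2 × (1.960 + 0.842)² × 2² / 0.5² ≈ 251.2, rounded up to 252, or 504 in total. The plan states 508 (127 in each of 4 cells, so 2 × 127 = 254 per method), which is consistent. Power at 254 per method is 0.804.

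**3. Illustration of a differential shift**

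Let b be the amount by which the interviewer effect differs between methods, with no true difference. The documents give no value for b; 0.1 and 0.2 points are assumptions.

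SE = 2 × √(2/254) = 0.1775.

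P(reject) = 1 − Φ(1.96 − b/SE) + Φ(−1.96 − b/SE).

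- b = 0: 0.05.
- b = 0.1: b/SE = 0.563, so P = [1 − Φ(1.397)] + Φ(−2.523) = 0.081 + 0.006 = 0.087.
- b = 0.2: b/SE = 1.127, so P = [1 − Φ(0.833)] + Φ(−3.087) = 0.202 + 0.001 = 0.203.

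This is a z-test on means. Section VIII plans multinomial mixed models for the survey questions, so these are not the planned analysis's error rates; they only show scale.

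**4. How many women a new rule would reach**

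Version 11 is dated 3/15/2019 and enrolment closes 5/31/2019: 16 + 30 + 31 = 77 days. The window opened June 1, 2016, so it spans 3 × 365 = 1,095 days, and 77/1,095 ≈ 7%.

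**The case against.** The strongest reply is that verbal surveying of women who cannot be blinded is a common pragmatic choice, and that role overlap is not personal overlap. The job title of nurse may cover many people, and the survey may come up to about two days later. This stands as far as it goes. The documents show that the same person may do both for one woman, not that this happens.

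Four stronger readings are tempting, and the documents support none of them.

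- A reader might infer that interviewers are known to be unblinded. No section says what an interviewer knows. It is an inference from the overlap of roles and the absence of any masking.
- A reader might infer that the bias favours the family-centered method. Section IX records the study team's hypothesis, not the views of bedside staff. Nurses give care in both arms, so courtesy answers could arise in both; an equal effect would mainly add noise or push scores towards the ceiling.
- A reader might infer that nothing collected could reveal the problem. The lists in Section VII cover the electronic record and the operating-room worksheet. The survey form is separate and may record the interviewer or carry instructions on administration. One can say only that no such record is visible in what was supplied.
- A reader might take a smaller SD and obtain more striking error rates: an SD of 1 would give 0.20 and 0.62 for the same two shifts. The documents offer no basis for that SD, so those figures carry no weight here.

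It is also fair to say that the mother's own expectations cannot be masked. That is a separate problem, which no choice of interviewer removes.

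**Conclusion.** The point holds in a limited form. The two sections name different interviewers and must be reconciled. The permitted roles overlap with those that consent and randomise and, for nurses, with those that give the differing newborn care. No independence requirement appears. The primary outcome is therefore open to interviewer bias, which matters for the comparison only if it differs by method.

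Its size and direction cannot be determined from the documents. The illustrative rates of about 0.09 and 0.20 rest on the assumed shifts of 0.1 and 0.2 points, the plan's SD of 2, full recruitment to 254 per arm, a two-sided 0.05 test and a simplified analysis. They are not evidence that the trial's result is biased. The case for acting is that the remedy is cheap, although its prospective reach is small.

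**What to change.** 1. Reconcile Sections III and VII in one statement that applies at both hospitals: the survey is asked by one of the staff already listed who took no part in that woman's consent, randomisation or delivery. The exclusion applies to the coordinator too.
2. Record interviewer role on each survey, and back-fill it for earlier surveys where records allow.
3. Add a sensitivity analysis of the primary outcome with an interviewer-role-by-method interaction. Role as a main effect alone cannot show bias that differs by arm. Interviewers are chosen after randomisation, so read the interaction as a diagnostic rather than a correction. Treat any coordinator-only subset as descriptive for the same reason.
4. State the limitation for surveys taken before the rule, since it covers only the enrolment remaining between 3/15/2019 and 5/31/2019.
5. Do not switch to self-completion now. A second survey mode this late would add a further difference between surveys for little gain.

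The cost is a wording change, one data field and one sensitivity analysis. Because the interviewer comes from the existing pool, no extra staff are needed. The downside is some scheduling effort and possibly a few missed surveys, in a trial whose Section VII already expects some to be incomplete.
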